7.1.2 Handling of Specimens

One 10 mL vial will be used for isolation of plasma via centrifugation for cytokine analysis and NMR analysis for metabolic signatures of immune activation. The remaining vials will be used for isolation of peripheral mononuclear cells (PBMCs) using Ficoll and cryopreserved until ready for analysis per standard protocol [66, 67]. For the PBMC isolated from 40ml of blood obtained prior to the start of adjuvant therapy, all will be used to isolate monocytes per standard protocol [67]. The isolated monocytes will be incubated with IL-4 and GM-CSF to produce dendritic cells (DC)[67], which will then be cryopreserved for analysis of tumorspecific functional activity of peripheral blood immune cells. To determine the phenotype of peripheral blood immune cells, following the 4-week interval, cryopreserved PBMC will be thawed and stained with labeled antibodies to CD4, CD8, CD45, CCR7, CD27, CD28, and CD62, markers of T cell hypofunctionality (e.g. PD-1, CTLA-4, LAG-3, TIM3, FoxP3, and ICOS), as well as MDSC (e.g. CD11b, CD33, CD14, CD15, Lin, HLA-DR). A subset of our analysis will be a comparison of CD8⁺PD-1⁺LAG-3⁺ T cells between before and after starting Optune and before and after starting pembrolizumab as this cell population has been shown to mark tumor-specific CD8⁺ T cells [68]. Cells will be assessed by flow cytometry in the Preston Wells, Jr. Center for Brain Tumor Therapy or by single cell genomics analysis for a comparison between before and after starting Optune and before and after starting pembrolizumab.

7.1.3 Transport of Specimens

Blood samples collected should be transported to [name] lab to be processed at ambient temperature immediately after collection and processed immediately upon arrival. If a delay in

transport or processing of greater than 1 hour is anticipated, samples must be stored on ice. Samples should be processed within 4 hours of collection.

7.2 Tumor Tissue Specimens

7.2.1 Collection of Specimens

Any flash frozen tissue (from either surgical resection or biopsy) available after histopathologic diagnosis of GBM, that will be collected for research purposes, will be obtained for priming of DC. Fixed and paraffin embedded samples will be obtained from pathology or research tissue banks for IHC.

7.2.2 Handling of Specimens

Tissue and PBMC cryopreservation are per standard protocol. FFPE samples will be used to test for PD-L1 IHC to be performed in [name] lab or the ICBR core lab. Flash frozen tumor samples will be minced and lysed into tumor lysate or treated with RNA buffer for total RNA isolation for DC priming. Parts of tissue will also be subjected to genomics analysis of the tissue to study the tumor immune microenvironment and correlate these findings with changes in immune systems related to Optune and Optune plus pembrolizumab.

7.2.3 Transport of Specimens

FFPE samples will be transported at room temperature. Frozen samples will be transported on dry ice or in liquid nitrogen to [name] lab.

Contact persons: [name] ([contact]) or [name] ([contact])

Frozen samples will be kept at-80°C until ready for processing.

7.3 Urine Specimens

7.3.1 Collection of Specimens

Approximately twenty milliliters of clean-catch urine will be collected into a sterile plastic cup prior to starting adjuvant therapy and within approximately 1 week before the first dose of pembrolizumab. Subsequently research urine will be collected prior to the second dose of pembrolizumab, and at approximately 2-, 4-, 6-, 12-, and 24-months (+/- 2 weeks) post-pembrolizumab. If study treatment is terminated due to disease progression or toxicity prior to the 24 months study term, a final urine sample will be obtained within 30 (+/- 7) days of progression.

7.3.2 Handling of Specimens

Urine samples will be stored at -80°C until analysis. Samples will be analyzed using NMR technique to detect metabolomic signatures of immune activation by comparing the pre-adjuvant/Optune samples to the post-adjuvant/Optune, but pre-pembrolizumab samples. These samples will be compared to the post-pembrolizumab samples.

7.3.3 Transport of Specimens

Urine samples will be transported to the [name] Lab on ice within 1 hour of collection.

8. ADVERSE REACTIONS AND DOSE DELAYS/DOSE MODIFICATIONS

8.1 Potential Adverse Events: Temozolomide

Treatment with TMZ commonly (\geq 10%) causes the following adverse reactions: alopecia, fatigue, nausea, vomiting, headache, constipation, anorexia, convulsions, rash, hemiparesis, diarrhea, asthenia, fever, dizziness, coordination abnormal, viral infection, amnesia, and insomnia.

Treatment with TMZ commonly ($\geq 10\%$) causes the following adverse reactions: lymphopenia, thrombocytopenia, neutropenia and leukopenia.

Adverse events and complications associated with the underlying GBM disease process, which are unlikely but unknown if related to treatment with Optune together with adjuvant TMZ include the following adverse events:

- Seizure, including Status Epilepticus
- Neurological and functional decline
- Headaches, nausea and/or vomiting
- Death

Table 1: Temozolomide Dose Levels for Adjuvant Treatment

Dose Level	Dose (mg/m2/day)	Remarks
-1	100	Reduction for prior toxicity
0	150	Dose during Cycle 1
1	Dose during Cycles 2-12 in ab of toxicity	

Table 2: Temozolomide Dose Reduction or Discontinuation During Adjuvant Treatment

Toxicity	Reduce TMZ by 1 Dose Level ^a	Discontinue TMZ
----------	---	-----------------

Absolute Neutrophil Count	<1.0 x 10 ⁹ /L	See footnote b
Platelet Count	<50 x 10 ⁹ /L	See footnote b
CTC Non-hematological Toxicity (Except for alopecia, nausea, vomiting)	CTC Grade 3-4	See footnote b

a: TMZ dose levels are listed in table 1.

8.2 Potential Adverse Events: Pembrolizumah

AEs associated with pembrolizumab exposure may represent an immunologic etiology. These immune-related AEs (irAEs) may occur shortly after the first dose or several months after the last dose of pembrolizumab treatment and may affect more than on body system simultaneously. Therefore, early recognition and initiation of treatment is critical to reduce complications. Based on existing clinical study data, most irAEs were reversible and could be managed with interruptions of pembrolizumab, administration of corticosteroids and/or other supportive care. For suspected irAEs, ensure adequate evaluation to confirm etiology or exclude other causes. Additional procedures or tests such as bronchoscopy, endoscopy, skin biopsy may be included as part of the evaluation. Based on the severity of irAEs, withhold or permanently discontinue pembrolizumab and administer corticosteroids. Dose modification and toxicity management guidelines for irAEs associated with pembrolizumab are provided in the Table 3 below.

b: TMZ is to be discontinued if dose reduction to <100 mg/m2 is required or if the same Grade 3 non-hematological toxicity (except for alopecia, nausea, vomiting) recurs after dose reduction.

TMZ = temozolomide; CTC = Common Toxicity Criteria.

Table 3: Pembrolizumab Dose Reduction or Discontinuation

General instructions:

- 1. Corticosteroid taper should be initiated upon AE improving to Grade 1 or less and continue to taper over at least 4 weeks.
- 2. For situations where pembrolizumab has been withheld, pembrolizumab can be resumed after AE has been reduced to Grade 1 or 0 and corticosteroid has been tapered. Pembrolizumab should be permanently discontinued if AE does not resolve within 12 weeks of last dose or corticosteroids cannot be reduced to ≤10 mg prednisone or equivalent per day within 12 weeks.
- **3.** For severe and life-threatening irAEs, IV corticosteroid should be initiated first followed by oral steroid. Other immunosuppressive treatment should be initiated if irAEs cannot be controlled by corticosteroids.

Immune-related AEs	Toxicity grade or conditions (CTCAEv4.0)	Action taken to pembrolizumab	irAE management with corticosteroid and/or other therapies	Monitor and follow-up
Pneumonitis	Grade 2	Withhold	Administer corticosteroids (initial dose of 1-2 mg/kg prednisone or equivalent) followed by taper	 Monitor participants for signs and symptoms of pneumonitis Evaluate participants with suspected
	Grade 3 or 4, or recurrent Grade 2	Permanently discontinue		 pneumonitis with radiographic imaging and initiate corticosteroid treatment Add prophylactic antibiotics for opportunistic infections
Diarrhea / Colitis	Grade 2 or 3	Withhold	Administer corticosteroids (initial dose of 1-2 mg/kg prednisone or equivalent) followed by taper	 Monitor participants for signs and symptoms of enterocolitis (ie, diarrhea, abdominal pain, blood or mucus in stool with or without fever) and of bowel perforation (ie, peritoneal signs and ileus). Participants with ≥ Grade 2 diarrhea
	Grade 4	Permanently discontinue		 suspecting colitis should consider GI consultation and performing endoscopy to rule out colitis. Participants with diarrhea/colitis should be advised to drink liberal quantities of clear fluids. If sufficient oral fluid intake is not feasible, fluid and electrolytes should be substituted via IV infusion.
AST / ALT elevation or	Grade 2	Withhold	Administer corticosteroids (initial dose of 0.5- 1 mg/kg prednisone or equivalent) followed by taper	Monitor with liver function tests (consider weekly or more frequently until liver

Increased bilirubin	Grade 3 or 4	Permanently discontinue	Administer corticosteroids (initial dose of 1-2 mg/kg prednisone or equivalent) followed by taper	enzyme value returned to baseline or is stable
Type 1 diabetes mellitus (T1DM) or Hyperglycemia	Newly onset T1DM or Grade 3 or 4 hyperglycemia associated with evidence of β-cell failure	Withhold	 Initiate insulin replacement therapy for participants with T1DM Administer anti-hyperglycemic in participants with hyperglycemia 	Monitor participants for hyperglycemia or other signs and symptoms of diabetes.
Hypophysitis	Grade 2	Withhold	Administer corticosteroids and initiate hormonal replacements as clinically indicated.	Monitor for signs and symptoms of hypophysitis (including hypopituitarism and adrenal insufficiency)
	Grade 3 or 4	Withhold or permanently discontinue ¹		, , , , , , , , , , , , , , , , , , ,
Hyperthyroidism	Grade 2	Continue	Treat with non-selective beta- blockers (eg, propranolol) or thionamides as appropriate	Monitor for signs and symptoms of thyroid disorders.
	Grade 3 or 4	Withhold or permanently discontinue ¹		
Hypothyroidism	Grade 2-4	Continue	Initiate thyroid replacement hormones (eg, levothyroxine or liothyroinine) per standard of care	Monitor for signs and symptoms of thyroid disorders.
Nephritis with Renal dysfunction	Grade 2 or 3 Increased blood creatinine	Withhold	Administer corticosteroids (prednisone 1-2 mg/kg or equivalent) followed by taper.	Monitor changes of renal function
	Grade 4 Increased blood creatinine	Permanently discontinue		
Exfoliative Dermatologic	Suspected SJS, TEN, or DRESS	Withhold	Administer corticosteroids (initial dose of 1-2 mg/kg prednisone or	Monitor participants for increase in lesion size or frequency during corticosteroid
Conditions	Confirmed SJS, TEN, or DRESS	Permanently discontinue	equivalent) followed by taper	course. Resume in patients with complete or partial resolution (Grades 0 to 1) after corticosteroid taper. Permanently discontinue if no complete or partial resolution within 12 weeks of initiating

				steroids or inability to reduce prednisone to 10 mg per day or less (or equivalent) within 12 weeks of initiating steroids.
Myocarditis	Grade 1	Withhold	Based on severity of AE administer corticosteroids	Ensure adequate evaluation to confirm etiology and/or exclude other causes
	Grade 2, 3, or 4	Permanently discontinue		
All other immune-related	Intolerable/ persistent Grade 2	Withhold	Based on type and severity of AE administer corticosteroids	Ensure adequate evaluation to confirm etiology and/or exclude other causes
AEs	Grade 3	Withhold or discontinue based on the type of event. Events that require discontinuation include and not limited to: Gullain-Barre Syndrome, encephalitis		
	Grade 4 or recurrent Grade 3	Permanently discontinue		

^{1.} Withhold or permanently discontinue pembrolizumab is at the discretion of the investigator or treating physician.

NOTE:

For participants with Grade 3 or 4 immune-related endocrinopathy where withhold of pembrolizumab is required, pembrolizumab may be resumed when AE resolves to \leq Grade 2 and is controlled with hormonal replacement therapy or achieved metabolic control (in case of T1DM).

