6.3 Temozolomide Administration

Patients will begin treatment with adjuvant TMZ at least 4 weeks but no more than 6 weeks from last dose of concomitant temozolomide or radiation therapy (the latter of the two). A minimum of 6 and maximum of 12 cycles of adjuvant TMZ will be given depending on tolerability and toxicity.

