6.3.1 Adjuvant Temozolomide Treatment

- Adjuvant Phase Cycle 1 (4-6 weeks after chemoradiation): Dosage in Cycle 1 will be 150 mg/m² PO daily for 5 consecutive days per 28 (+7) day cycle.
- Cycle 2 (up to Cycle 12): At the start of Cycle 2, the dose of TMZ will be increased to 200 mg/m² PO daily for 5 consecutive days per 28 (+7) day cycle, if the CTC nonhematologic toxicity for Cycle one is Grade ≤ 2 (except for alopecia, nausea and vomiting), absolute neutrophil count (ANC) is ≥ 1.5 x 10⁹/L, and the platelet count is ≥ 100 x 10⁹/L. The TMZ dose will remain at 200 mg/m² PO daily for 5 consecutive days per 28 (+7) day cycle for each subsequent cycle except if toxicity occurs (see section 8.1). If the dose is not increased at Cycle 2 due to toxicity, escalation should not occur in subsequent cycles; however, it is appropriate to decrease to cycle 1 dose in cycles 2-12 if toxicity occurs.

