6.4 Follow-Up Evaluations During The 12 Cycles of Adjuvant TMZ

All patients will be seen before Cycle 1 of TMZ, before starting the pembrolizumab, and every 3 weeks (+/-4 days) before each subsequent pembrolizumab dose at an outpatient clinic until they complete all 12 cycles of adjuvant TMZ or discontinue TMZ due to toxicity or first progression. Optune compliance reports will be collected remotely or in the clinic setting approximately every 4 (+/- 1) weeks. Contiguous data will be sufficient for Optune compliance reporting, per SOC for the Optune Device.

At each visit the following will be performed except otherwise specified:

- Physical exam and performance status (KPS)
- Blood exams
 - o CBC with differential within 3 days prior to starting each cycle of temozolomide
 - Complete Metabolic Panel prior to each cycle of pembrolizumab and prior to starting each cycle of temozolomide (+/- 7 days)
 - o PT/PTT, INR for patients receiving relevant anti-coagulants
 - o TSH, Free T4 prior to the first infusion of pembrolizumab and then prior to every other pembrolizumab infusion thereafter
- Study lab as specified
- Steroid dose
- Concomitant Medications
- Record of Adverse Events
- TTF compliance report (only every 4 +/- 1 weeks)

An MRI will be performed every 2 months (+/- 7 days) following the baseline MRI until second progression (when study treatment will be terminated). In the case of clinical progression an unscheduled MRI will be obtained within 1 week of the investigator becoming aware of the clinical progression. Contrast agent type and dose will be kept constant for each patient between scans. Disease will be assessed as per iRANO criteria [64] [65] with allowance for potential immune mediated effects at first appearance. No additional MRIs will be required by the study after second progression. Medical follow-up will continue for 30 (+/- 7) days after treatment termination in

order to capture treatment related toxicities. After this visit, mortality will be assessed based on telephone interviews with the patients or the patients' caregivers every 3 months.

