6.6 Post Treatment Evaluations

Treatment will continue according to the protocol until toxicity, second progression or 24 months (the earlier of the three). After treatment termination the patient will be followed every three months via phone call or collected from clinic notes for survival follow up until death or for 5 years, whichever occurs first.

Subjects will be evaluable for survival analysis if they have received Optune treatment, AND have received at least one dose of pembrolizumab, AND have received adjuvant temozolomide. Subjects that are not evaluable for survival analysis will be replaced.

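### Temozolomide stopping rule: a recurrent Grade 3 non-hematological toxicity forces a stop, but on the 200 to 150 mg/m2 path a recurrent Grade 4 does not

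*Combined protocol and SAP*

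**What the plan says.** Section 6.3.1 starts adjuvant temozolomide at 150 mg/m2 in Cycle 1 and raises it to 200 mg/m2 at Cycle 2 if Cycle 1 was tolerated. After that, "The TMZ dose will remain at 200 mg/m² PO daily for 5 consecutive days" per cycle, "for each subsequent cycle except if toxicity occurs (see section 8.1"). Patients held back at Cycle 2 stay off the higher dose: "If the dose is not increased at Cycle 2 due to toxicity, escalation should not occur in subsequent cycles".

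Section 8.1 holds the toxicity rules. Table 1 lists 150 mg/m2 as level 0 and 100 mg/m2 as level -1. Table 2 has one row for non-hematological toxicity (alopecia, nausea and vomiting excepted). It prescribes a one-level reduction for Grades 3 and 4 alike and sends the discontinuation decision to footnote b.

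Footnote b has two limbs:

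- **Dose floor:** "TMZ is to be discontinued if dose reduction to <100 mg/m2 is required".
- **Recurrence:** or "if the same Grade 3 non-hematological toxicity (except for alopecia, nausea, vomiting) recurs after dose reduction".

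Other sections mention stopping for toxicity without naming a grade. Section 6.3: "A minimum of 6 and maximum of 12 cycles of adjuvant TMZ will be given depending on tolerability and toxicity". Section 6.4 refers to patients who "discontinue TMZ due to toxicity or first progression". Section 6.6: "Treatment will continue according to the protocol until toxicity, second progression or 24 months".

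**The concern.** The reduction column names Grades 3 and 4. The recurrence limb of the footnote that governs stopping names Grade 3 only. Read as written, the mandatory stop applies to a severe toxicity that comes back and not to a life-threatening one (Section 9.12, Table 5, gives the grade definitions). That reverses the order expected of a safety rule, and the protocol gives no reason for it.

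A patient could have two Grade 4 episodes of the same toxicity and be given temozolomide again at 100 mg/m2 with no protocol deviation. Whether that happens would rest on the treating investigator's judgment, which is what a mandatory rule is meant to replace. With mixed grades, two investigators could act differently on identical facts and both be compliant.

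**Working it through.** There is no plan figure to reproduce. The check traces the rule through each dose path and each pair of grades.

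**Inputs**

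- Dose levels: 200 mg/m2 (Section 6.3.1; the level 1 dose cell of Table 1 is not legible in the text copy), 150 and 100 mg/m2 (Table 1).
- Reduction: one level for Grade 3 or 4 (Table 2).
- Stops: the two limbs of footnote b.
- Course length: 6 to 12 cycles, 5 dosing days each (Sections 6.3 and 6.3.1).

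**Path 200 to 150 mg/m2.** After the first event the patient is on 150. If the same toxicity recurs, the next level is 100. That is not below 100, so the dose-floor limb is not met and only the recurrence limb can force a stop. Its words Grade 3 could describe the first event (A), the recurrence (B) or both (C).

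| First event, then recurrence | A | B | C |
|---|---|---|---|
| Grade 3, Grade 3 | stop | stop | stop |
| Grade 3, Grade 4 | stop | 100 | 100 |
| Grade 4, Grade 3 | 100 | stop | 100 |
| Grade 4, Grade 4 | 100 | 100 | 100 |

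Stops: 2 + 2 + 1 = 5 of 12 cells; the other 12 − 5 = 7 continue at 100 mg/m2. Grade 3 then Grade 3 stops on all three readings. Grade 4 then Grade 4 continues on all three. Each mixed sequence continues on two of three.

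**Path 150 to 100 mg/m2.** After the first event the patient is on 100. Any recurrence at Grade 3 or 4 would need a dose below 100, so the dose-floor limb stops treatment whatever the grade: 12 of 12 cells stop. Patients not escalated at Cycle 2 because of toxicity never receive 200 mg/m2, so they cannot be on the affected path.

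**Further exposure on the affected path.** Dose per cycle = 100 mg/m2 × 5 days = 500 mg/m2. The first event at 200 mg/m2 can occur no earlier than Cycle 2, so the recurrence falls in Cycle r with r ≥ 3. Further cycles = N − r, where N is the planned number of cycles.

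- N = 6: r = 3 to 5 gives 6 − 3 = 3 down to 6 − 5 = 1 cycles, or 3 × 500 = 1,500 down to 500 mg/m2.
- N = 12: r = 3 to 11 gives 12 − 3 = 9 down to 12 − 11 = 1 cycles, or 9 × 500 = 4,500 down to 500 mg/m2.

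The upper figures are ceilings. They need the two events in Cycles 2 and 3, no third event, and no stop on judgment.

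**The case against.** The strongest reply is that Grade 3 here is shorthand for Grade 3 or worse. Table 2 sends both grades to footnote b, and on that threshold reading all four sequences stop. This may well be what the authors meant. It is not how the protocol writes elsewhere, where ranges and thresholds are spelled out:

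- The Table 2 row served by this footnote names both grades.
- Section 6.3.1 sets its escalation condition with an explicit at-most-Grade-2 limit.
- Section 14.1.1 states its reporting threshold as Grade 2 and above.
- The catch-all row of Table 3 for pembrolizumab lists Grade 4 alongside recurrent Grade 3 as grounds for permanent discontinuation. Footnote b has the recurrent Grade 3 part and no Grade 4 part.

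The second reply is that safeguards exist. Once the patient is on 100 mg/m2, another Grade 3 or 4 event triggers the dose floor, so the rule allows at most one extra dose level. A life-threatening event is a serious adverse event (Section 9.11.2) and must reach the investigator within 24 hours (Section 14.1.1). Investigators may also stop temozolomide on judgment. All of this stands, and it limits the harm. None of it is a mandatory stop at the second Grade 4 event.

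It is also fair that the route is narrow. It needs a patient who tolerated Cycle 1 well enough to escalate, two Grade 4 episodes of one non-hematological toxicity, and an investigator willing to re-treat.

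**Conclusion.** The concern holds. As written, footnote b is stricter for the milder recurrence than for the worse one. The defect is confined to patients reduced from 200 to 150 mg/m2. There, a repeated Grade 4 toxicity leads to 100 mg/m2, or 500 mg/m2 per further cycle, where a repeated Grade 3 leads to none; the two mixed sequences are ambiguous.

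This rests on taking Grade 3 as an exact grade, in line with the protocol's usage elsewhere. If the sponsor meant a threshold, the intended rule is sound and only its wording is at fault; the same edit is needed. The number of patients affected is unknown and probably small. The primary and secondary endpoint definitions and the sample-size calculation are untouched.

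**What to change.** Amend the recurrence limb of footnote b in two places: after the words Grade 3 insert **or 4**, and after the verb recurs insert **at Grade 3 or higher**. Leave the dose-floor limb unchanged.

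On the 200 to 150 mg/m2 path all 12 cells in the table above then become stops. The 150 to 100 mg/m2 path does not change. A Grade 4 toxicity that returns only at Grade 2 or lower does not trigger a mandatory stop.

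The cost is seven words (2 + 5) in the next amendment, with no new tests or visits. The clinical price is that a rare patient with recurrent Grade 4 toxicity, or with a mixed Grade 3 and 4 recurrence now read as allowing continuation, stops temozolomide one dose level earlier.
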